
Variables:
 
Exposures
 
 
• Olodaterol/Tiotropium Bromide (Stiolto®) delivered via Respimat inhaler
 
• Umeclidinium/Vilanterol (Anoro®) delivered via Ellipta Inhaler
 
 
Outcome
 
 
• Discontinuation of index treatment (Olodaterol/Tiotropium Bromide or Umeclidinium/Vilanterol), defined as persistence of treatment (no refill claim within 60 days (allowable grace period) after end of <n> days supply). Addition of another drug will not count as a discontinuation.
 
 
Covariates
 
Demographics
 
 
• Age on the cohort entry date
 
• Sex (Male, Female)
 
• Region (Northeast, North Central, South, West, Unknown, Missing)
 
• Insurance Type (Commercial, Medicare, Missing)
 
• Study Year of Cohort Entry (First Year: 17 Nov 2015-30 Nov 2016, Second Year: 01 Dec 2016-30 Nov 2017, Third Year: 01 Dec 2017-31 Mar 2018)
 
 
Concomitant Medications
 
 
• Oral Corticosteroids (OCS)
 
• Short acting muscarinic antagonist (SAMA)
 
• Short acting beta agonist (SABA)
 
• Long acting muscarinic antagonist (LAMA)
 
• Long acting beta agonist (LABA)
 
• Inhaled corticosteroid (ICS)
 
• LAMA / LABA combination (that is not Stiolto or Anoro)
 
• LABA / ICS combination
 
• LAMA / LABA / ICS combination
 
• NSAIDs
 
• Antihistamines
 
			

Name of company: Boehringer Ingelheim International GmbH			
Name of finished medicinal product: Stiolt® Respimat®; Anoro® Ellipta®			
Name of active ingredient: Olodaterol and Tiotropium Bromide (ATC R03AL06); Umeclidinium and Vilanterol (ATC R03AL03)			
Protocol date: 22 November 2019	Study number: 1237-0090	Version/Revision: 1.0	Version/Revision date: NA

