## **9. RESEARCH METHODS**

### **9.1 STUDY DESIGN**

The proposed study will utilize data from the Truven MarketScan dataset (US).

The Truven MarketScan databases are comprised of two components: the MarketScan Commercial Claims and Encounters (CCAE) Database and the Medicare Supplemental and Coordination of Benefits (COB) Database. These databases capture longitudinal, individual-level data on healthcare utilization, healthcare expenditures and plan enrollment, and contain integrated records for patient demographics, inpatient events, outpatient events, and pharmacy dispensing of drugs. The CCAE database is a medical and drug insurance claims database on ~150 million patients since from 2008 unique de-identified patients that include active employees, dependents, retirees or recipients of the Consolidated Omnibus Budget Reconciliation Act (COBRA), and data are drawn from large employers, health plans, and public organizations in the United States (Truven Health MarketScan® Research Databases 2015). The MarketScan Medicare Supplemental and Coordination of Benefits (COB) Database contains pooled medical and drug insurance claims data of approximately 13.6 Million unique de-identified patients (since 1996) that are Medicare-eligible retirees with employer-sponsored Medicare Supplemental plans. (**Truven Health MarketScan® Research Databases 2015**).

In principle, in US when a patient goes to a pharmacy and gets a drug dispensed, the pharmacy bills the insurance carrier for the cost of that drug (**Strom 2013**). For billing purposes, the pharmacy has to identify which medication was dispensed along with the dosage strength (e.g. the milligrams per tablet) and quantity (e.g., number of tablets, etc.). Analogously, when a patient goes to a hospital or to a physician for medical care, the providers of care bill the insurance carrier for the cost of the medical care, and have to justify the bill with a diagnosis. Using a common patient identification number for both the pharmacy and the medical care claims, these elements can be linked, and analyzed as a longitudinal medical record (**Strom 2013**).

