**9.4 DATA SOURCES**

The proposed study will utilize data from Truven MarketScan data (US).

The Truven MarketScan databases capture longitudinal, individual-level administrative claims data from the United States. The data available for the study includes three components of MarketScan: the Commercial Claims and Encounters (CCAE) Database, the Medicare Supplemental and Coordination of Benefits Database (MDCR), and the Medicaid Database. Patients in the databases include active employees, dependents, retirees, COBRA recipients, and Medicare or Medicaid enrollees. Data were drawn from large employers, health plans, and public organizations in the United States. The following tables of the MarketScan databases were available for analysis: Enrollment Detail, Inpatient Admissions, Inpatient Services, Outpatient Services, Outpatient Pharmaceutical Claims, and Long Term Care. These tables provide information on plan enrollment, healthcare utilization and expenditures, demographics, and integrated records for inpatient events, outpatient events, and pharmacy dispensings. Data are available from January 1, 2008 to March 31, 2018, and represent approximately 162 million patients.

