#### 9.7.1.1 Descriptive Analysis

All variables specified in [section 9.3.3](#) will be reported. For demographic and lifestyle variables, the value recorded on the cohort entry date will be reported, otherwise the most recent known value will be reported. Presence of comorbidities and use of concomitant medication use will be determined based whether they ever occurred within the 180-day baseline period preceding the index date. Differences in the confounder distributions were inspected for successful confounder balance of measured characteristics.

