### 9.7.2 Sensitivity Analysis

Four sensitivity analyses will be conducted. For these analyses, in the interest of reducing the number of additional tables, only the descriptive statistics for the matched population ([Annex Table 2](#)), and primary results ([Annex Tables 4](#) and [5](#)) will be reported.

Two sensitivity analyses will be conducted to evaluate the robustness of the outcome definition:

1. Use of a 30-day Grace Period

Restrict the 60-day allowable grace period used to define the discontinuation outcome to 30 days to allow a gap of one month. This sensitivity analysis may be useful if the 60-day grace period is too lenient, as the usual day's supply of Stiolto is 30 days.

2. Use of a 90-day Grace Period

Since neither the Olodaterol/Tiotropium Bromide or Umeclidinium/Vilanterol drug products are available as generic formulations, the relatively high price of these medications may lead some patients to space out their doses to greater than the recommended dosing schedule or use one puff instead of two to prolong their medication supply. Patients may also neglect to take their medications due to forgetfulness or because they become less symptomatic. Thus, we will also increase the 60-day allowable grace period used to define the discontinuation outcome, to 90 days.

Two sensitivity analyses will be conducted in an attempt to increase the sample size:

3. Start Patient Identification Period in 21 May 2015

The primary identification period starts 180 days after Stiolto Respimat was approved by FDA for use in the US (21 May 2015) on 17 November 2015. This sensitivity cohort will start the patient identification period immediately upon FDA approval on 21 May 2015.

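### The covariates do not measure benefit design within payer or prior refill behaviour, so a difference between arms in either would go unseen and unbalanced and could be read as a device effect

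*Combined protocol and SAP*

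**What the plan says.** The primary outcome (Section 4, Variables; Section 9.3.2.1) is discontinuation, defined as "no refill claim within 60 days (allowable grace period) after end of <n> days supply". Any sufficiently long gap between fills counts, whatever its cause.

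In justifying the 90-day grace period, Section 9.7.2 (item 2) states that "the relatively high price of these medications may lead some patients to space out their doses to greater than the recommended dosing schedule", and adds: "Patients may also neglect to take their medications due to forgetfulness or because they become less symptomatic".

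The only payer covariate in the Abstract and Section 9.3.3 is "Insurance Type (Commercial, Medicare, Missing". For baseline drugs, Section 9.7.1.1 says: "Presence of comorbidities and use of concomitant medication use will be determined based whether they ever occurred within the 180-day baseline period". Sections 9.2.2 (Matched Cohort) and 9.7.1.3 build the propensity score and the multivariable models from the Section 9.3.3 list. The matched Cox model contains treatment alone.

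On the data held, Section 9.1 describes "individual-level data on healthcare utilization, healthcare expenditures and plan enrollment", and Section 9.4 says of the available tables: "These tables provide information on plan enrollment, healthcare utilization and expenditures". Section 9.6 takes drug duration from the days'-supply field.

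**The concern.** The plan itself names two influences on dosing that can lengthen refill gaps, and then measures neither at baseline. If what patients pay within a payer, or how reliably they refill, differed between the two products, it would be associated with both exposure and outcome, and the matched hazard ratio would carry it.

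Two features make this more than a routine caveat. First, Tables 2 and 3 report balance only on listed variables, so they could look excellent while these factors are unbalanced. Second, the title and rationale ask whether the inhaler device plays a role in persistence, so any residual difference is likely to be attributed to the device. Section 9.12 relies on matching to control confounding by observable covariates. Refill history looks observable from data already held, and so do at least proxies for benefit design.

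**Working it through.** **Step 1: is the gap real?** The lists in Sections 4 and 9.3.3, the definitions in Annexes 3 and 4, and Tables 2 and 3 contain no plan type, cost-sharing, refill-gap or days-covered variable. The nearest items are insurance type, region, entry year, and influenza and pneumococcal vaccination. Section 9.4 also lists Medicaid as a data component, but insurance type has no Medicaid level.

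**Step 2: does another analysis close it?** No. The multivariable models use the same covariate list. The four sensitivity analyses change the grace period (30 or 90 days), the start date, or the asthma exclusion. A longer grace period applies equally to both arms and does not balance them.

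**Step 3: the plan's own figure.** 3,889 + 10,862 = 14,751, as stated in Section 9.5. The plan gives no event rate, effect size or power, so everything below rests on assumptions.

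**Step 4: precision.** A full 1:2 match needs 2 × 3,889 = 7,778 of the 10,862 comparators, 11,667 patients in all. This is the upper limit. With proportion p discontinuing (assumed),

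SE(log HR) = √[1/(3,889p) + 1/(7,778p)].

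| p | SE(log HR) | 95% CI is HR multiplied or divided by |
|---|---|---|
| 0.40 | 0.0311 | 1.063 |
| 0.50 | 0.0278 | 1.056 |
| 0.70 | 0.0235 | 1.047 |

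An estimate about 5-6% from 1 would therefore exclude 1.

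**Step 5: bias from an omitted binary factor.** Let the factor have prevalence p1 and p0 in the two arms and multiply the hazard of discontinuation by H. With no true difference, the spurious HR is

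B = (p1·H + 1 − p1) / (p0·H + 1 − p0).

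The last two columns use ln(B)/SE, with the chance of a false difference taken from the normal distribution at two-sided 5%.

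| p1 v p0 | H | B | ln(B)/SE at p = 0.50 | False difference, p = 0.40 to 0.70 |
|---|---|---|---|---|
| 25% v 20% | 1.3 | 1.075/1.060 = 1.014 | 0.5 | 7-9% |
| 30% v 20% | 1.5 | 1.15/1.10 = 1.045 | 1.6 | 30-47% (36% at 0.50) |
| 40% v 20% | 2.0 | 1.40/1.20 = 1.167 | 5.5 | near 100% |

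B is the hazard ratio at time zero. Averaged over a one-year Cox fit (constant hazards, no censoring before one year), the middle case falls to 1.041-1.043, which does not change the picture.

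**The case against.** The strongest reply is that the exposure side of the confounding path is missing. Nothing in the documents mentions formularies, tiers or copayments that differ between the two products, and no mechanism is given by which past refill behaviour would steer a patient to one inhaler. Section 9.7.2 treats the products alike, as neither has a generic. That stands: the documents neither show nor exclude an imbalance.

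A reader might infer that the plan admits price makes patients stop refilling, or that the 90-day analysis is a failed attempt to control confounding. Neither is supported. The text speaks of stretching supply and neglecting doses, and the 90-day analysis addresses misclassification of such gaps, which is a reasonable aim.

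Partial control also deserves credit. The design compares new users of two branded drugs in one class, requires medical and pharmacy coverage of everyone, and matches on insurance type, region, entry year and age. Vaccination is a weak proxy for health-seeking behaviour. Any bias must come from differences left after these.

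Finally, Section 9.9 concedes that unmeasured and residual confounding cannot be ruled out. That is fair, but it is generic, names neither factor, and does not explain leaving out variables that the described data appear able to supply.

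**Conclusion.** The point holds as an omission in the covariate set, worth correcting. It is not a demonstrated bias. The outcome is a refill gap, the plan names price and forgetfulness as influences on dosing, and neither benefit design within payer nor prior refill behaviour is measured, although relevant data are described as available.

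It would go too far to conclude that the primary hazard ratio is confounded: the arms are not shown to differ, and the direction is unknown. The spurious HR ranges from 1.014 to 1.167 over the inputs tried, with about 1.045 (1.6 standard errors) in the middle case. At the low end the false-positive rate is barely above 5%. These figures rest wholly on assumed prevalences, hazard ratios and event proportions, and on a full 1:2 match. They show only that, with intervals this narrow, a modest imbalance could matter.

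**What to change.** Add two baseline variables to Section 9.3.3, and so to the propensity score, the multivariable models and Tables 2 and 3:

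1. Health-plan type, from the enrolment data.
2. Proportion of days covered in the 180-day baseline for maintenance drugs already listed, as a categorical variable with an explicitly defined level for patients with no baseline maintenance fills. State that this level is not missing data under Section 9.6, so that the exclusion rule for variables with more than 75% missing does not apply to it.

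If patient-paid amounts are in the licensed data (the documents say only expenditures), add as a sensitivity analysis a baseline cost-sharing measure that does not depend on drug mix, such as the patient-paid share of total drug cost. An average paid per 30 days across all drugs would partly measure which drugs the patient takes. Do not match on the cost of the index fill, which is partly a feature of the product.

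In Section 9.9, name cost sharing and prior adherence as possible residual confounders.

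The cost is a few more derived covariates, a possible sensitivity run, protocol wording, and perhaps a small loss of matches. If no cost fields are held, the two main variables can still be built from the enrolment and days'-supply data.

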Name of company: Boehringer Ingelheim International GmbH			
Name of finished medicinal product: Stiolto® Respimat®; Anoro® Ellipta®			
Name of active ingredient: Olodaterol and Tiotropium Bromide (ATC R03AL06); Umeclidinium and Vilanterol (ATC R03AL03)			
Protocol date: 22 November 2019	Study number: 1237-0090	Version/Revision: 1.0	Version/Revision date: NA
Data sources:	Truven MarketScan is a claims database that captures longitudinal, individual-level administrative claims data from the United States.		
Study size:	There are 14,751 new users of Olodaterol/Tiotropium Bromide or Umeclidinium/Vilanterol between 17 November 2015 and 31 March 2018 who satisfied the inclusion criteria. Among them, 3,889 initiated Olodaterol/Tiotropium Bromide and 10,862 initiated Umeclidinium/Vilanterol).		
Data analysis:	
For demographic and lifestyle variables, the value recorded on the cohort entry date will be reported, otherwise the most recent known value will be reported. Presence of comorbidities and use of concomitant medication use will be determined based whether they ever occurred within the 180-day baseline period preceding the index date. Differences in the confounder distributions will be inspected for successful confounder balance of measured characteristics.
 
Patients will be followed up until first occurrence of death, discontinuation, disenrollment, end of data, or 365 days.
 
The data will be displayed in a nonparametric fashion on a persistency curve (a Kaplan–Meier curve) with discontinuation considered as elimination.
 
Unmatched Cohort Rates and risks (proportion of patients) with the outcomes for each exposure group will be reported among the unmatched cohort.
 
Matched Cohort Rates and risks (proportion of patients) with the outcomes for each exposure group will be reported among the matched cohort.
 
Logistic regression will be used to calculate the propensity to initiate Olodaterol/Tiotropium Bromide versus Umeclidinium/Vilanterol. The propensity score will then be used to identify up to 2 initiators of Umeclidinium/Vilanterol for each initiator of Olodaterol/Tiotropium Bromide with the same propensity score (<math>\pm</math> a caliper of 5%) as the corresponding initiator of Olodaterol/Tiotropium Bromide.
		

Name of company: Boehringer Ingelheim International GmbH			

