### **9.2 SETTING**

#### **9.2.1 Definitions**

Study Period: the period of time that includes the exclusion criteria assessment period, baseline, cohort entry date, and follow-up period for the study population. This period is the same for all patients.

The study period will be from 1 January 2008 to 31 March 2018, encompassing date of the earliest data availability to the date of the latest data availability.

Patient Selection Period: the period of time for which patients are eligible to enter the cohort. The earliest date of the patient selection period is 17 November 2015, corresponding to 180-days after US approval date of Stiolto Respimat.

Cohort Entry Date: Date of entry to the initial cohort of Stiolto or Anoro users.

[figure not shown]
Baseline Period: the 180-day period that ends 1 day prior to the cohort entry date used to assess covariate information. The baseline period will vary between patients depending on these dates. The earliest start of the baseline period would be 21 May 2015, the date of Stiolto approval (i.e. 180 days before November 17, 2015).

Follow-Up Period: the period of time between 1 day after the cohort entry date to the earliest occurrence of the outcome (discontinuation of refills), or any censoring criteria (365 days, death, disenrollment, or end of data). Addition of another treatment in addition to index treatment will not count as discontinuation.

For entry into the study population, patients will be required to have 180 days of continuous enrolment with both medical and pharmacy coverage. Data during the baseline period will be used to confirm study eligibility and classification of incident COPD. The follow-up period will be used for capturing first and second maintenance therapies. This is illustrated in **Figure 1**.

Figure 1

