#### **9.3.3 Covariates**

Covariates will be identified based on data recorded within 180 days prior to or on the index date (date of dispensing/initiation of the exposure), unless otherwise specified. If multiple measurements are made in the baseline period, then the most recent measurement will be used.

Covariates will be used to predict propensity scores in later analyses. Absolute and relative frequencies of each covariate will also be reported in Table Shells 1 and 2 (see [Annex 5](#)). Detailed descriptions of the listed covariates can be found in [Annex 3](#) and [4](#).

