Heart Failure	
1 Inpatient
 
Diagnosis Code (Any Position), ICD-9 is any of: { “428”, “428.0”, “428.1”, “428.2”, “428.20”, “428.21”, “428.22”, “428.23”, “428.3”, “428.30”, “428.31”, “428.32”, “428.33”, “428.4”, “428.40”, “428.41”, “428.42”, “428.43”, “428.9” }
 
Diagnosis Code (Any Position), ICD-10 is any of: { “I50”, “I50.9”, “I50.2”, “I50.20”, “I50.21”, “I50.22”, “I50.23”, “I50.3”, “I50.30”, “I50.31”, “I50.32”, “I50.33”, “I50.4”, “I50.40”, “I50.41”, “I50.42”, “I50.43” }

Hypertension	
1 Inpatient or 2 Outpatient (30 – 365 days apart)
 
Diagnosis Code (Any Position), ICD-9 is any of: { “401”, “401.0”, “401.1”, “401.9”, “402”, “402.0”, “402.00”, “402.1”, “402.10”, “402.9”, “402.90”, “403”, “403.0”, “403.00”, “403.01”, “403.1”, “403.10”, “403.11”, “403.9”, “403.90”, “403.91”, “404”, “404.0”, “404.00”, “404.01”, “404.02”, “404.03”, “404.1”, “404.10”, “404.11”, “404.12”, “404.13”, “404.9”, “404.90”, “404.91”, “404.92”, “404.93”, “405”, “405.0”, “405.01”, “405.09”, “405.1”, “405.11”, “405.19”, “405.9”, “405.91”, “405.99” }
 
Diagnosis Code (Any Position), ICD-10 is any of: { “I10”, “I11.9”, “I12.0”, “I12.9”, “I13.0”, “I13.10”, “I13.11”, “I13.2”, “I15.0”, “I15.8” }

Upper Respiratory Infection (with no sinusitis)	
1 Inpatient or 2 Outpatient (30 – 365 days apart)
 
Diagnosis Code (Any Position), ICD-9 is any of: { “034”, “034.0”, “034.1”, “460”, “461”, “461.0”, “461.1”, “461.2”, “461.3”, “461.8”, “461.9”, “462”, “463”, “464”, “464.0”, “464.00”, “464.01”, “464.1”, “464.10”, “464.11”, “464.2”, “464.20”, “464.21”, “464.3”, “464.30”, “464.31”, “464.4”, “464.5”, “464.50”, “464.51”, “465”, “465.0”, “465.8”, “465.9”, “487”, “487.1”, “487.8” }
 
Diagnosis Code (Any Position), ICD-10 is any of: { “J03.00”, “J03.01”, “A38”, “A38.8”, “A38.9”, “J00”, “J01”, “J01.9”, “J01.90”, “J01.8”, “J01.80”, “J01.0”, “J01.00”, “J01.01”, “J32.0”, “J01.1”, “J01.10”, “J01.11”, “J32.1”, “J01.2”, “J01.20”, “J01.21”, “J32.2”, “J01.3”, “J01.30”, “J01.31”, “J32.3”, “J02”, “J02.8”, “J02.9”, “J04”, “J04.0”, “J05”, “J05.0”, “J04.1”, “J04.10”, “J04.11”, “J04.2”, “J05.1”, “J05.10”, “J05.11”, “J04.3”, “J04.30”, “J04.31”, “J06”, “J06.9”, “J11.89”, “J11.8”, “J11.1”, “J11”, “J10.89”, “J10.8”, “J10.1”, “J10.00”, “J10.0”, “J10”, “J09.X2”, “J09.X9”, }

	“J09.X”, “J09” }

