Charlson-Deyo Comorbidity Index	
This measure computes a score by summing over the following components:
 
 
· If the event Acute Myocardial Infarction Occurs within 180 days, set the score to 1.0 Otherwise, set the score to 0.0
 
· If the event Heart Failure Occurs within 180 days, set the score to 1.0 Otherwise, set the score to 0.0
 
· If the event Peripheral Vascular Disease Occurs within 180 days, set the score to 1.0 Otherwise, set the score to 0.0
 
· If the event Cerebrovascular Disease Occurs within 180 days, set the score to 1.0 Otherwise, set the score to 0.0
 
· If the event Dementia Occurs within 180 days, set the score to 1.0 Otherwise, set the score to 0.0
 
· If the event Chronic Obstructive Pulmonary Disease Occurs within 180 days, set the score to 1.0 Otherwise, set the score to 0.0
 
· If the event Rheumatologic Disease Occurs within 180 days, set the score to 1.0 Otherwise, set the score to 0.0
 
· If the event Peptic Ulcer Disease Occurs within 180 days, set the score to 1.0 Otherwise, set the score to 0.0
 
· If the event Hemiplegia or Paraplegia Occurs within 180 days, set the score to 2.0 Otherwise, set the score to 0.0
 
· If the event Renal Disease Occurs within 180 days, set the score to 2.0 Otherwise, set the score to 0.0
 
· If the event HIV/AIDS Occurs within 180 days, set the score to 6.0 Otherwise, set the score to 0.0
 
· For the measure Cancer use the value of the measure as the score multiplied by weight 1.0 If the value is missing, set the score to 0.0
 
· For the measure Diabetes use the value of the measure as the score multiplied by weight 1.0 If the value is missing, set the score to 0.0
 
· For the measure Liver Disease use the value of the measure as the score multiplied by weight 1.0 If the value is missing, set the score to 0.0
 

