## **ANNEX 5. TABLE SHELLS AND PROPOSED FIGURES**

**Table 1.** Cohort Selection

	Excluded	Remaining
Eligible Population		
Did not meet cohort entry criteria (use of Tio/Olo or Ume/Vi)		
< 180 days of continuous enrollment		
Prior use of Ume/Vi during 180d washout		
Prior use of Tio/Olo during 180d washout		
Tio/Olo and Ume/Vi both occurring on cohort entry date		
Age <40 years		
No prior diagnosis of COPD any time prior using all available data		
Diagnosis of Asthma any time prior using all available data		
Diagnosis of Lung Cancer any time prior using all available data		
Lung Transplant any time prior using all available data		
Final cohort		

**Table 2.** Patient Characteristics of the Study Population (Unmatched/ Matched)

	Tio/Olo	Umech/Vi	Standardized Difference (95% CI)
N			
Median Follow-up Time [IQR]			
Demographics			
Age on index date			
Mean (SD)			
Median [IQR]			
Gender			
Male; n (%)			
Female; n (%)			
Region			
Northeast; n (%)			
North Central; n (%)			
South; n (%)			
West; n (%)			
Missing/Unknown; n (%)			
Insurance Type			
Commercial; n (%)			
Medicare; n (%)			
Missing; n (%)			
Year of Cohort Entry, n (%)			
First Year (November 17, 2015 – November 30, 2016); n (%)			
Second Year (December 1, 2016 – November 30, 2017); n (%)			
Third Year (December 1, 2017 to March 31, 2018)			
Concomitant Medications			

Proprietary confidential information © 2019 Boehringer Ingelheim International GmbH or one or more of its affiliated companies

	Tio/Olo	Umec/Vi	Standardized Difference (95% CI)
Oral Corticosteroids; n (%)			
Short acting muscarinic antagonist (SAMA), n (%)			
Short acting beta agonist (SABA), n (%)			
Long acting muscarinic antagonist (LAMA), n (%)			
Long acting beta agonist (LABA), n (%)			
Inhaled corticosteroid (ICS), n (%)			
LAMA / LABA combination (not Tio/Olo or Umec/Vi), n (%)			
LABA / ICS combination, n (%)			
LAMA / LABA / ICS combination, n (%)			
NSAIDs, n (%)			
Antihistamines, n (%)			
Opioids, n (%)			
Oral antibiotics, n (%)			
Antidiabetic Agents (not including insulin), n (%)			
Insulin (basal or mealtime), n (%)			
Methotrexate, n (%)			
Statins; n (%)			
Antihypertensives; n (%)			
Anticoagulants; n (%)			
Anti-psychotic/anti-depressives/anxiolytic, n (%)			
Oxygen therapy, n (%)			
Comorbidities/Symptoms			
History of All-Cause Hospitalization; n (%)			
History of Emergency Department Visit; n (%)			

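### Two-claim confirmation of lasting comorbidities does not fit the 180-day covariate window, so stable outpatients coded less often than about every three months are increasingly missed

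*Combined protocol and SAP*

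**What the plan says.** Four places set the window. The Abstract (Data analysis) and Section 9.7.1.1 say comorbidities are "determined based whether they ever occurred within the 180-day baseline period preceding the index date". Section 9.3.3 restricts the data themselves: "Covariates will be identified based on data recorded within 180 days prior to or on the index date", with an allowance for exceptions stated elsewhere. Section 9.2.1 defines baseline as "the 180-day period that ends 1 day prior to the cohort entry date used to assess covariate information". Sections 9.2.1 and 9.3.3 therefore differ on whether the index date counts.

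Annex 4 sets the confirmation rule. For hypertension, depression, anxiety, osteoporosis, chronic kidney disease, diabetes and many others it is "1 Inpatient or 2 Outpatient (30 – 365 days apart". In the Charlson row most components carry the same window, for example "If the event Peripheral Vascular Disease Occurs within 180 days, set the score to 1.0". The cancer, diabetes and liver components take the value of another measure and have no 180-day phrase.

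For eligibility the plan looks further back. Section 9.2.2 defines asthma and lung cancer by the same one-inpatient or two-outpatient rule, and Table 1 of Annex 5 applies it over the full history: "Diagnosis of Asthma any time prior using all available data". Section 9.4 states that "Data are available from January 1, 2008 to March 31, 2018". On prior enrolment, Section 9.2.1 says only that "patients will be required to have 180 days of continuous enrolment with both medical and pharmacy coverage".

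**The concern.** A rule that accepts two claims up to 365 days apart is paired with a window that cannot hold two claims more than about 179 days apart. A patient whose hypertension is coded at six-monthly visits satisfies the Annex 4 definition, yet on a literal reading of Section 9.3.3 has no qualifying pair in the data used. The short window is not forced by the database, since the same rule runs over all prior data for asthma and lung cancer.

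The flags are used in three ways. Hypertension, depression, anxiety and osteoporosis enter the propensity model (Section 9.2.2) and the unmatched multivariable models (Section 9.7.1.3) as separate terms. Conditions that are Charlson components, such as peripheral vascular disease and dementia, are left out as separate terms and act only through the score. All of them appear in the baseline tables that serve the first secondary objective. The matched Cox model has treatment as its only term, so nothing downstream makes up for a confounder that was poorly measured at matching. Tables 2 and 3 test balance on the flags as coded, so they can look satisfactory while the underlying conditions remain unbalanced. A flag that needs two coded visits in six months also partly measures how often a patient is seen.

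**Working it through.** **The plan's own date.** 17 November 2015 minus 180 days is 21 May 2015, the earliest baseline start given in Section 9.2.1. It reproduces.

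**How many covariates are affected.** Section 9.3.3 lists 34 entries under Comorbidities/Symptoms, and Annex 4 gives 24 of them the two-outpatient rule. Three of the 24 are acute infections (upper respiratory, lower respiratory, pneumonia). The other 24 - 3 = 21 are mostly lasting conditions. Not affected are, among others, acute myocardial infarction, arrhythmia and acute liver injury (one claim suffices), heart failure and cerebrovascular disease (inpatient claim only), and reflux disease (its own rule).

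**Largest spacing the window can hold.** From day -180 to day -1 is 179 days, or 180 if the index date counts. The rule accepts 365 - 30 + 1 = 336 whole-day spacings. Those from 180 to 365 days number 186, and 186/336 = 55%, so about half of the accepted spacings cannot occur inside baseline.

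**Data available.** From 1 January 2008 to the first entry date of 17 November 2015 is 2,877 days.

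**Capture of a stable outpatient.** Assumptions: the condition is coded at outpatient visits every T days, the start is random, and there is no inpatient claim. The documents give no visit intervals, so a range is shown.

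- Strict reading, both claims in days -180 to -1. For T from 90 to 180, capture = 180/T - 1; above 180 it is zero.
- Alternative reading, second claim in baseline and the other possibly before day -180. For T up to 365, capture = min(1, 180/T), provided the patient was enrolled at the earlier visit.

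| T (days) | Strict | Second claim in baseline |
|---|---|---|
| 90 | 180/90 - 1 = 100% | 100% |
| 91 | 180/91 - 1 = 98% | 100% |
| 122 | 180/122 - 1 = 48% | 100% |
| 150 | 180/150 - 1 = 20% | 100% |
| 182 | 0% | 180/182 = 99% |
| 183 | 0% | 180/183 = 98% |
| 365 | 0% | 180/365 = 49% |

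Under the strict reading the loss starts just beyond three-monthly coding and is complete at six-monthly coding. Using all prior data captures 100% at each of these spacings if enrolment is long enough.

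**Irregular visits.** In a simulation with a mean gap of 182.5 days and a standard deviation of 7 to 30 days, the strict reading captured 1% to 6% and the second-claim-in-baseline reading 93% to 98%. The result does not depend on exact regularity.

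**The case against.** The strongest reply is that the plan never says both claims must fall inside baseline. The Abstract and Section 9.7.1.1 ask whether the comorbidity occurred in the window, and the Charlson row asks whether the event did. An event confirmed by a second claim in baseline, with the other dated before day -180, could fit that wording. On that reading nearly all six-monthly patients with enough history are flagged. This stands as a limit: a reader might infer that such patients are always coded disease-free, and the documents do not settle that. Section 9.3.3, which restricts the data themselves, favours the strict reading, and no section states the alternative.

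Second, a reader might infer that every affected condition enters the models as its own flag. Sections 9.2.2 and 9.7.1.3 exclude Charlson components as separate terms, and chronic kidney disease overlaps the renal component.

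Third, a reader might attach a size to the confounding. If true prevalence were 30% v 24% and a flag had 20% sensitivity and perfect specificity, exact matching on it alone would leave 84% of the imbalance; at 94.5% sensitivity, 7%. The documents support neither figure. The prevalences and sensitivities are assumed, inpatient claims are ignored, and antihypertensives, antidiabetics, insulin, statins, psychotropic drugs and prior hospital use are also in the model. The lower figure also presumes about three years of prior enrolment, whereas the plan requires 180 days.

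Fourth, a fixed window equal to the minimum enrolment gives every patient the same look-back, and eligibility is a different purpose from confounder measurement. That is a legitimate trade-off, and it weighs against requiring all prior data in the primary analysis. But the plan does not argue it, does not list it in Section 9.9 or 9.12, and varies it in none of the four sensitivity analyses.

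**Conclusion.** The mismatch is real and worth correcting before the analysis. Read literally, Sections 9.3.3 and 9.7.1.1 and the Abstract make about half of the claim spacings accepted by Annex 4 unusable, for 24 of the 34 listed comorbidity entries. Capture falls from about 98% at 91-day coding to 48% at 122 days and 0% at 182 days, assuming regular outpatient coding and no inpatient claim. The covariates are therefore less sensitive than their definitions intend, the baseline description is understated, and the balance tables cannot show it.

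The documents do not show that the hazard ratio is materially biased, or in which direction. That depends on visit frequency, on true differences between the groups, and on how far medication covariates and inpatient claims make up the loss. The supported conclusion is avoidable under-ascertainment and an unstated rule for claim pairs that straddle day -180.

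**What to change.** In the Abstract, Section 9.3.3, Section 9.7.1.1 and the Charlson row of Annex 4, state that claims before day -180 count towards the 30-to-365-day rule for lasting conditions. At minimum, accept any pair whose second claim falls in baseline, even if the other is dated before day -180. Say which look-back the cancer, diabetes and liver components of the Charlson score use. Keep 180 days for medications, utilisation, acute events and tests. Reconcile Sections 9.2.1 and 9.3.3 on whether the index date is included.

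Add to Section 9.7.2 a sensitivity analysis that ascertains lasting conditions from all prior data, with length of prior enrolment as a covariate. Report the strict 180-day version alongside.

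The cost is protocol wording and a re-run of existing measures on data already held, with no loss of patients. The downside is that look-back then varies with prior enrolment. A patient with only 180 days of history gains nothing, and the enrolment covariate can balance length between groups but does not fully correct misclassification that varies with it.
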